7.3 Phone Calls

Subjects will be called sometime after the Baseline Visit to remind them to go to a Quest Diagnostics laboratory to have blood draw for urate level assessment per written schedule that they were given at the Baseline Visit. Subjects should have blood drawn in the morning just prior to scheduled dose (trough level).

Week 3 blood draw to monitor urate level will occur 21 ± 3 days after the Baseline Visit.

Week 6 blood draw to monitor urate level will occur 42 ± 3 days after the Baseline Visit.

Week 9 blood draw to monitor urate level will occur 63 ± 3 days after the Baseline Visit.

Week 16 blood draw to monitor urate level will occur $112 \text{ days} \pm 3$ days after the Baseline Visit.

The Phone Calls will take place approximately one-seven days after each blood draw and the following procedures will be performed:

- Review results of the urate level test

- Instruct subject to continue the same dose of inosine or modify dose to target urate levels
- Review and document concomitant medications and therapies
- Assess and document AEs

7.4 Week 12 Visit

This visit will take place 84 ± 3 days after the Baseline Visit. This visit should occur in the morning and subjects should hold their morning dose to obtain uric acid trough level. The following will be performed:

- Measure vital signs, including weight
- Collect blood samples for clinical laboratory assessments (urate level, safety labs)
- Collect urine for urinalysis
- Administer ALSFRS-R questionnaire
- Perform Pulmonary Function Tests (SVC)
- Columbia Suicide Severity Rating Scale (C-SSRS) – Since Last Visit
- Review and document concomitant medications and therapies
- Assess and document AEs
- Dispense study medication and dosing diary
- Perform study drug accountability and collect all unused study drug and empty containers

7.5 Week 20 Visit

This visit will take place 140 ± 7 days after the Baseline Visit. This visit should occur in the morning and subjects should hold their morning dose to obtain uric acid trough level. The following will be performed:

- Measure vital signs, including weight
- Collect blood samples for clinical laboratory assessments (urate level, safety labs)
- Collect urine for urinalysis
- Administer ALSFRS-R questionnaire
- Perform Pulmonary Function Tests (SVC)
- Columbia Suicide Severity Rating Scale (C-SSRS) – Since Last Visit
- Review and document concomitant medications and therapies
- Assess and document AEs
- Collect study drug and dosing diary
- Perform study drug accountability and collect all unused study drug and empty containers
- Uninstall mobile app

7.6 Week 24 Phone Call

A follow-up phone call will take place $28 + 5$ days after the subject's last dose of study drug. The following will be performed:

- Complete ALSFRS-R Questionnaire
- Review and document concomitant medications and therapies
- Assess and document AEs

7.7 Final Safety Visit

Subjects who early terminate from the study and do not wish to be followed per protocol off study drug will be asked to come in for a Final Safety Visit and will be asked to have a final Follow-Up Telephone Call (+ 5 days, but no earlier than 28 days, after subject's last dose of study drug).

The following will be performed at the Final Safety Visit:

- Measure vital signs, including weight
- Collect blood samples for clinical laboratory assessments (urate level, safety labs)
- Administer ALSFRS-R questionnaire
- Perform Pulmonary Function Tests (SVC)
- Columbia Suicide Severity Rating Scale (C-SSRS) – Since Last Visit
- Review and document concomitant medications and therapies
- Assess and document AEs
- Collect study drug and dosing diary
- Perform study drug accountability and collect all unused study drug and empty containers
- Uninstall mobile app.

The following procedures will be performed via telephone 28 + 5 days after the Final Safety Visit:

- Administer ALSFRS-R questionnaire
- Review and document concomitant medications and therapies
- Assess and document AEs

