This study will be conducted in subjects who meet the El Escorial criteria of possible, laboratory-supported probable, probable, or definite criteria for a diagnosis of ALS. At screening, eligible subjects must be at least 18 years old and must provide written informed consent prior to screening. Subjects on a stable dose of riluzole and those not taking riluzole, and women of child-bearing age at screening are eligible for inclusion as long as they meet specific protocol requirements. Detailed criteria are described in the body of the protocol.

Treatment Plan

Subjects will be administered oral inosine daily. The dose of inosine will be titrated to obtain serum urate levels of 7 - 8 mg/dL.

Duration of Treatment and Follow-up

Subjects will remain on treatment until the Week 20 visit. Each subject will also have a Week 24 Follow-up Telephone Interview to assess for adverse events (AEs), changes in concomitant medications and to administer the ALSFRS-R.

SCHEDULE OF ACTIVITES

Activity	Screening Visit ¹	Baseline	Week 3, 6 and 9 Phone Call and Urate Test	Week 12	Week 16 Phone Call and Urate Test	Week 20	Week 24 Phone Call	Final Safety Visit (for early study drug discontinuation only)
Visit Names	Visit 1	Visit 2	Visits 3, 4, and 5	Visit 6	Visit 7	Visit 8	Visit 9	
Visit Window	-21 days from Day 0	Day 0	± 3 days	± 3 days	± 3 days	± 3 days	± 3 days	
Written Informed Consent	X							
Inclusion/Exclusion Review	X	X						
Medical History/Demographics	X							
ALS Diagnosis History	X							
Physical Examination	X							
Neurological Exam	X							
Vital Signs ² / Height & Weight ³	X			X		X		X
Screening Labs ⁴	X							
C-SSRS		X		X		X		X
Uric acid level ⁵		X	X	X	X	X		X
Urine alkalization protocol (if needed per protocol)		X		X				
Urinalysis ⁶		X		X		X		X
Basic Metabolic Panel	X							
Safety Labs ⁷		X		X		X		X
ALSFRS-R ⁸		X		X		X	X	X
Pulmonary Function Testing ⁸	X			X		X		X
Concomitant Medication Review	X	X	X	X	X	X	X	X
Adverse Event Review	X	X	X	X	X	X	X	X
Dispense Study Drug		X		X				
Drug Accountability				X		X		X
Exit Questionnaire						X		X
Mobile app installation ¹⁰		X						
Mobile app un-installation ¹⁰						X		X

¹ Screening procedures must be completed within 21 days prior to Baseline Visit.

² Vital signs include systolic and diastolic pressure in mmHg, respiratory rate/minute, heart rate/minute and temperature.

³ Height measured at Screening Visit only.

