4.3 Study Duration

Subjects will remain on treatment until the Week 20 visit. Each subject will also have a Week 24 Follow-up Telephone Interview to assess for adverse events (AEs), changes in concomitant medications and to administer the ALSFRS-R.

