5.3.1 Handling of Withdrawals

A subject may choose to discontinue participation in the study at any time. However, the Site Investigator or designee will encourage subjects to continue with follow-up, regardless of their compliance with study drug. If a subject who initiated study drug permanently discontinues study drug, the SI or designee should still encourage subjects to follow the study protocol under the

modified intent-to-treat principle (ITT). These subjects will be encouraged to follow the study visits, off drug, up to the final visit. Loss to follow-up should be prevented whenever possible.

Any subject who is on study drug and needs to begin the use of any prohibited medication, must immediately discontinue use of study drug. Subjects who permanently discontinue study drug should return any unused study drug and complete early study drug discontinuation procedures per protocol.

If a subject wishes to withdraw consent, i.e., withdraw his or her participation in future study procedures, the subject will be asked to delay consent withdrawal to allow for a final safety visit and final safety telephone call. The subject will be asked to return to the study site for a final safety visit within 14 days of asking to withdraw consent. The subject will also be asked to have a final telephone call 28 days (+ 5 days) after taking their last dose of study drug.

In the event a subject no longer wishes to have their personal health information used for the analysis of this study, he or she will notify the site through an authorized letter and his or her data will no longer be included as part of the results for this study.

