6.3.2. Dosage Discontinuation

Reasons for discontinuation of study medication may include an AE, Medical Monitor or Principal Investigator recommendation, protocol deviation, loss-to-follow-up, subject request, or death.

Study subjects who discontinue study drug prematurely (early termination from study) will be encouraged to return for a Final Safety Visit and participate in a Follow-Up Telephone Call 28 days (+ 5 days) after the last dose of study drug.

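### The rules for subjects who stop study drug early conflict on who attends the Final Safety Visit, whether urine is tested, when the last call falls, and whether Week 24 contact occurs

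*Combined protocol and SAP*

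**What the plan says.** **Who is seen.** The Schedule of Activities heads the column "Final Safety Visit (for early study drug discontinuation only"). Section 6.3.2 reads "Study subjects who discontinue study drug prematurely (early termination from study) will be encouraged to return for a Final Safety Visit". The introduction to section 7 gives the visit to those who withdraw consent or terminate early. Section 7.7 is narrower: "Subjects who early terminate from the study and do not wish to be followed per protocol off study drug will be asked" to attend. Section 5.3.1 encourages subjects who stop drug to keep attending visits off drug, and says that they should "complete early study drug discontinuation procedures per protocol", without naming the visit for all of them.

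**Urine.** The Schedule marks urinalysis at the Final Safety Visit, and section 9.4 has urine collected at in-person visits. The 7.7 list has blood sampling but no urine item, whereas the lists in 7.4 and 7.5 have both.

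**Final call.** The first paragraph of 7.7 counts at least 28 days from last dose. Its last paragraph says "The following procedures will be performed via telephone 28 + 5 days after the Final Safety Visit". Section 6.3.2 has subjects "participate in a Follow-Up Telephone Call 28 days (+ 5 days) after the last dose of study drug". The Study Workflow note, 5.3.1, the section 7 introduction and 8.1.5 also count from last dose or stopping drug.

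**Week 24.** Section 4.3 says "Each subject will also have a Week 24 Follow-up Telephone Interview to assess for adverse events (AEs"), and the Schedule gives Visit 9 a window of ±3 days. Section 7.6, headed as the Week 24 call, says "A follow-up phone call will take place" 28 + 5 days after last dose and makes no exception for early stoppers. Section 10.2.2.1 compares adverse event proportions over 24 weeks by Fisher's exact test. Only its negative binomial sensitivity analysis adjusts for length of follow-up.

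**The concern.** Safety and tolerability are the primary outcomes of a trial of about 30 subjects, so each early stopper carries weight. Sites can apply the rules differently while each believes that it is following the protocol. Under 7.7, a subject who stops drug and stays in follow-up has no scheduled visit at stopping. A subject who does attend the visit may have no urinalysis. Under 7.6, a subject who stops and stays may have no adverse event contact in the last weeks of the analysis window. If stopping differs by arm, the unadjusted 24-week proportions would then rest on unequal observation, with under-counting in the arm that has more stoppers.

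**Working it through.** **1. The plan's own detection figure.** Section 10.2.2.5 states 80% power to see at least one event with true probability 8%. The formula is 1 − (1 − 0.08)^n. With 2:1 randomization of 30 (section 4.1), n = 20 on inosine, and 1 − 0.92^20 = 81.1%, which reproduces the figure. The 15 per arm in the Study Workflow would give 1 − 0.92^15 = 71.4%, which does not. I use n = 20.

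**2. Gap in urine and safety labs for a subject who stops just after the Week 3 call and stays.** The Week 3 draw is on day 21 ± 3, so day 18–24, and the call follows 1–7 days later, so day 19–31 (section 7.3). Week 12 is day 84 ± 3, so day 81–87 (section 7.4). The shortest gap is 81 − 31 = 50 days and the longest is 87 − 19 = 68 days. Serum urate is still drawn at Week 6 and Week 9.

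**3. Where the 7.6 call falls.** Day 0 is Baseline and Week 24 is day 24 × 7 = 168. The call is on the last-dose day + 28 to + 33. Nominal days:

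| Last dose | 7.6 call (day) | Days short of day 168 | Wait for next scheduled urinalysis and safety labs, if no visit at stopping |
|---|---|---|---|
| Week 3 (day 21) | 49–54 | 114–119 | 63 days (to day 84) |
| Week 6 (day 42) | 70–75 | 93–98 | 42 days (to day 84) |
| Week 9 (day 63) | 91–96 | 72–77 | 21 days (to day 84) |
| Week 12 (day 84) | 112–117 | 51–56 | 56 days (to day 140) |
| Week 16 (day 112) | 140–145 | 23–28 | 28 days (to day 140) |

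A subject who stays still has adverse event review at every scheduled contact to Week 20 (day 140). What a literal 7.6 removes is therefore at most about Weeks 20–24: 168 − 140 = 28 days, or 4 of 24 weeks. For a stop after Week 16 the call itself falls later than Week 20, and the loss is smaller.

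**4. The two anchors in 7.7.** From last dose, the call is at 28–33 days. From a Final Safety Visit held 14 days after last dose, it is at 14 + 28 = 42 to 14 + 33 = 47 days. The 14 days is the limit that 5.3.1 sets for the visit after a request to withdraw consent. I assume that the request coincides with the last dose.

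**5. Effect on detection power.** The documents do not give the number of inosine subjects who stop and stay, k, so I assume 1 to 6 of 20. The range is guided by 5% not tolerating treatment at 6 months in the cited Parkinson's disease trial (20 × 0.05 = 1) and by the 71% tolerant proportion in 10.2.2.5 (20 × 0.29 = 5.8). With constant hazard over 24 weeks, each such subject contributes 20/24 of full cover, and power is 1 − 0.92^(20 − k × 4/24):

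- k = 1: 80.9%
- k = 4: 80.1%
- k = 6: 1 − 0.92^19 = 79.5%

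The largest loss is 81.1 − 79.5 = 1.6 points. Lost observation at k = 6 is 6 × 4 = 24 of 20 × 24 = 480 inosine person-weeks, or 5%.

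**The case against.** The strongest reply is that these are wording slips with little consequence, because other parts of the protocol fill the gaps. Much of that stands.

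- A reader might infer that a site following 7.7 loses all stone and renal evidence at stopping. It does not for anyone who attends: urate and safety labs are on the list, safety labs include the Basic Metabolic Panel, and stones and gouty arthritis are events of special interest found by questioning. Only urine evidence is lost.
- A subject who stops for an adverse event and stays is not left unassessed. Section 6.3 follows all events to resolution, 8.1.2 allows extra tests, and 9.3 requires discontinuation to be reported within 24 hours. What is missing is a scheduled visit.
- A reader might blame the conflict for short cover in subjects who leave. Their cover ends about 28–33 days after last dose under the Study Workflow note, 5.3.1, 6.3.2 and the section 7 introduction as well. The visit-anchored call in 7.7 would lengthen it.
- The 3–5 day return of urate, reported in one small multiple sclerosis study in section 2.3.1, might suggest that the on-drug state is lost. The argument does not fit: the visit may fall up to 14 days after a withdrawal request, and in the Week 3 example a trough urate was drawn shortly before the call.
- Section 8.1.2 does not name the Final Safety Visit for any test, so its silence on urinalysis is not a separate contradiction.
- The documents do not show that early stoppers are the likeliest to have had a stone. In the cited Parkinson's disease trial no participant withdrew because of an adverse event.

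None of this reconciles 7.7 with the Schedule and 6.3.2, removes the double anchor, or makes 7.6 agree with 4.3. The sensitivity analysis adjusts for follow-up length, but the primary Fisher comparison does not.

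**Conclusion.** The point holds as four contradictions that need reconciling, with modest consequences that differ by group. Subjects who stop and stay have no scheduled visit at stopping under 7.7, with 50–68 days to the next scheduled urine and safety labs in the Week 3 example. Under 7.6 they also have no adverse event contact after Week 20 if they stopped by about Week 16. Subjects who leave and attend the visit lose only the urinalysis. The final call can differ by up to 14 days between the two anchors.

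The effect on detection power is small, at most about 1.6 points. That rests on 20 inosine subjects, an assumed six who stop and stay, and a constant hazard. The hazard assumption probably overstates the loss of drug-related events, since the lost weeks are off drug. The reason to act is that the primary safety window is 24 weeks and, as written, the contacts do not cover it for every subject still in follow-up.

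**What to change.** - Reconcile 7.7 with the Schedule, 6.3.2 and the section 7 introduction on who attends the Final Safety Visit, and state in 5.3.1 which procedures it means for subjects who stop drug but stay.
- Add urinalysis with sediment to the 7.7 list, to match the Schedule and 9.4.
- Use one anchor for the 28-day call throughout.
- In 7.6, time the Week 24 contact from Baseline for everyone still in follow-up, and keep the 28-day post-dose call for early stoppers as a separate contact, so that adverse event collection matches the window in 10.2.2.1.

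The cost is a wording amendment and, for the few subjects affected, at most one visit already in the Schedule, one urine sample and one telephone call.

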7.8 Protocol Deviations

A protocol deviation is any noncompliance with the clinical trial protocol. The noncompliance may be either on the part of the subject, the Site Investigator, or the study site staff. As a result of deviations, corrective actions are to be developed by the site and implemented promptly.

All deviations from the protocol must be addressed in the subject's source documents. All major protocol deviations will be entered in the Protocol Deviations Log in the Electronic Data Capture (EDC) System and should be submitted to the site's local IRB per institutional guidelines.

7.8.1 Missed Visits and Procedures

Missed visits and any procedures not performed (not attempted) for reasons other than screen failure, illness, injury or progressive disability (i.e. subject is physically unable to perform test) will be reported as protocol deviations.

Procedures or visits not performed due to screen failure, illness, injury or disability, including procedures that were attempted but failed (i.e. blood samples unable to be drawn after multiple attempts, or weight unable to be obtained due to subject immobility) will not be reported as protocol deviations.

Details and specific instructions regarding protocol deviations, including any exceptions to this standard procedure, are found in the Site Manual of Procedures.

7.9 Recording Deaths

Information on whether a subject has died may be obtained by the subject's family, clinic notes, or utilizing public means such as a reliable internet source such as the Centers for Disease Control and Prevention (CDC) National Death Index (<http://www.cdc.gov/nchs/ndi.htm>) or the Social Security Death Index (<http://ssdmf.info/>).

8 CLINICAL ASSESSMENTS AND OUTCOME MEASURES

8.1 Clinical Variables

Assessments will be performed at designated time-points throughout the study for clinical evaluation. In addition to the assessments evaluated below, subjects will provide information on their demographics, past medical history, including ALS, as well as concomitant medication usage.

8.1.1 Vital Signs, Height & Weight

Vital signs will be obtained after the subject has been in a seated position for several minutes. Vital signs, including systolic and diastolic blood pressure, pulse rate (radial artery)/minute, respiratory rate/minute, temperature and weight will be assessed at specified visits. Height will be measured and recorded at the Screening Visit only.

8.1.2 Clinical Laboratory Assessments

The following laboratory tests will be performed during the study:

- Serum urate level (Screening, Baseline, Weeks 3, 6, 9, 12, 16 and 20)
- Urinalysis: albumin, bilirubin, blood, clarity, color, glucose, ketones, nitrate, pH, protein, specific gravity, urobilinogen and WBC screen (Screening, Baseline, Week 12 and Week 20 visits). Urine sediment analysis will be also performed at the Baseline, Week 12 and Week 20 visits.
- Serum human chorionic gonadotrophin (hCG) for women of childbearing potential (WOCBP) (Screening ONLY)
- Hematology with differential panel: complete blood count with differential (hematocrit, hemoglobin, platelet count, RBC indices, Total RBC, Total WBC, and WBC & differential) (Baseline, Week 12 and Week 20)
- Blood chemistry panel/Liver function tests (LFTs): alanine aminotransferase (ALT (SGPT)), aspartate aminotransferase (AST (SGOT)), albumin, alkaline phosphatase, bicarbonate, blood urea nitrogen, calcium, chloride, creatinine, glucose, magnesium, phosphate, potassium, sodium, total bilirubin and total protein (Screening, Baseline, Week 12 and Week 20)

Additional testing, may be ordered if needed, to further assess an adverse event (AE), or if there is any suspicion that a subject may be pregnant, throughout the course of the study.

8.1.3 Physical Examination

A physical examination will be performed and recorded. The following systems will be examined: head/neck, eyes, ears, nose/throat, cardiovascular, lungs, abdomen, musculoskeletal, central nervous system, extremities, and skin.

8.1.4 Neurological Examination

A neurological examination will be performed and recorded.

8.1.5 Adverse Events

Adverse events (AEs) will be documented at each study visit, including the Screening Visit once the informed consent form has been signed by the subject, and at all study visits, including the final telephone call 28 days after the last dose of study drug. Information on adverse effects of study medication and on inter-current events will be determined at each visit by direct questioning of the subjects and review of concomitant medications.

8.1.6 ALSFRS-R

The ALSFRS-R is a quickly administered (5 minutes) ordinal rating scale (ratings 0-4) used to determine subjects' assessment of their capability and independence in 12 functional activities. All 12 activities are relevant in ALS. Initial validity was established by documenting that in ALS patients, change in ALSFRS-R scores correlated with change in strength over time, was closely associated with quality of life measures, and predicted survival. The test-retest reliability is greater than 0.88 for all test items. The advantages of the ALSFRS-R are that the categories are relevant to ALS, it is a sensitive and reliable tool for assessing activities of daily living function in those with ALS, and it is quickly administered. With appropriate training the ALSFRS-R can be administered with high inter-rater reliability and test-retest reliability. The ALSFRS-R can be administered by phone with good inter-rater and test-retest reliability. The equivalency of phone versus in-person testing, and the equivalency of study subject versus caregiver responses have also recently been established. Therefore, if necessary, the ALSFRS-R may be given to the study subject over the phone. All ALSFRS-R evaluators must be NEALS certified.

8.1.7 Pulmonary Function Testing

Pulmonary Function Testing includes Slow Vital Capacity (SVC).

Slow Vital Capacity (SVC): The vital capacity (VC) (percent of predicted normal) will be determined, using the upright slow VC method. The VC can be measured using conventional spirometers that have had a calibration check prior to subject testing. A printout from the spirometer of all VC trials will be retained. Three VC trials are required for each testing session, however up to 5 trials may be performed if the variability between the highest and second highest VC is 10% or greater for the first 3 trials. Only the 3 best trials are recorded on the CRF.

